8.6. Vital Signs

Vital signs and changes from baseline will be summarized descriptively by treatment group over time. The changes from baseline at each post-baseline on-treatment visit will be additionally summarized by dose level at visit.

Patients will also be categorized into the following groups for each of the vital sign parameters if a post baseline value falls into a specific group. Unscheduled assessments will be included in the determination. The number of subjects in each group will be summarized for each dosing group.

Diastolic Blood Pressure

- ≤ 50 mmHg
- ≥ 100 mmHg

Systolic Blood Pressure

- ≤ 80 mmHg
- ≥ 160 mmHg

Heart Rate

- ≤ 50 beats/min
- ≥ 120 beats/min

Respiratory Rate

- > 18 breaths/min

8.7. Electrocardiogram

The baseline ECG is defined as the mean of all pre-dose assessments. PR, RR, QRS, QT, and Fridericia corrected QT (QTcF) intervals and their change from baseline will be summarized by treatment group and scheduled assessment. Patients will be categorized into the following groups per their maximum change from baseline in QTcF. Unscheduled assessments will be included in the determination of the maximum change. The number and percentage of subjects in each group will be summarized.

- ≤ 30 msec
- $>30 - 60$ msec
- >60 msec

Patients will also be categorized into the following groups per their maximum post baseline QTcF. Unscheduled assessments will be included in the determination of the maximum post baseline value. The number of subjects in each group will be summarized for each dosing group.

- ≤ 450 msec
- $>450 - 480$ msec
- $>480 - 500$ msec
- >500 msec

ECG morphology analyses will be performed. New onset findings will be presented as the percentage of subjects with 'new' finding (ECG finding that were not present at any baseline ECG and became present on at least 1 ECG during the treatment) for the following variables

2:1 AV Block, AV Mobitz I,II, Complete heart block, first degree AV block, left atrial abnormality, left ventricular hypertrophy, right ventricular hypertrophy, incomplete left bundle branch block, incomplete right bundle branch block, intraventricular conduction defect, left anterior hemiblock, left bundle branch block, left posterior hemiblock, right bundle branch block, Wolff-Parkinson-White, Artificial pacemaker, atrial pacing, sinus bradycardia, sinus pauses, sinus tachycardia, atrial fibrillation, atrial flutter, atrial tachycardia, supraventricular tachycardia, prolonged QTC, ST depressed, ST elevated, T wave inverted, non-sustained ventricular tachycardia, ventricular fibrillation.

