4. TRIAL DESIGN

4.1. Overall Design

This is a Phase 3, randomized, placebo-controlled, double-blind, multi-center trial in patients with symptomatic oHCM. Approximately 270 eligible patients will be randomized in a 1:1 ratio to receive CK-3773274 or placebo. Randomization will be stratified by use of beta-blockers (yes or no) and CPET exercise modality (treadmill or bicycle) and implemented in the Interactive Web Response System (IWRS). A cap on the number of patients taking beta-blockers and will not exceed approximately 70% of total enrollment. The number of patients taking disopyramide will be capped at approximately 10% of total enrollment. The number of patients with persistent atrial fibrillation at screening will also be capped at approximately 15%, and the number of patients using the bicycle CPET exercise modality will be capped at approximately 50% as well.

IP will be administered orally once daily with or without food. During the initial six weeks of the treatment period, IP doses will be individually titrated at Weeks 2, 4, and 6 using echocardiography. Dose escalation at Weeks 2, 4, and 6 will occur only if a patient has a post-Valsalva LVOT-G ≥ 30 mmHg and a biplane LVEF $\geq 55\%$. Echocardiograms will be performed at each subsequent visit during the trial and the dose down titrated if necessary. The primary endpoint of pVO₂ will be measured by CPET at screening and at end of treatment (Week 24). Patients' background HCM therapy should be individually optimized according to the local practice.

All patients will be followed according to the Schedule of Activities (SoA) from randomization through the date of their final visit irrespective of whether the patient is continuing to receive IP, unless the patient has discontinued prematurely from the trial or withdrawn consent. An early discontinuation visit will be performed for patients who discontinue prematurely from the trial.

The overall study design is described by a trial schema in [Figure 2](#).

The trial endpoints and objectives are defined in [Table 2](#).

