9.4. Statistical Analyses

The Statistical Analysis Plan (SAP) will be finalized prior to database lock and it will include a more technical and detailed description of the statistical analyses described in this section. This section is a summary of the planned statistical analyses of the most important endpoints including primary and key secondary endpoints.

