9.4.1. General Considerations

Summary tables will present descriptive statistics such as number of patients, mean, median, standard deviation, minimum and maximum for continuous variables, and number of patients and the percentage for categorical variables, overall and by treatment in the planned analysis sets. For model-based analysis, least squares means (LSMs), difference of LSMs between treatments, their standard errors and 95% confidence intervals (CI), and two-sided p-values for the relative statistical inferences will be presented. Baseline is defined as the last available measurement taken before the first dose of randomized IP unless otherwise specified. Listings will include patient ID, demographics, treatment assigned and other relevant items, and sorted by treatment assignment, patient ID and date of assessment. Unless specified otherwise, efficacy, safety and pharmacokinetics analyses will be performed on the full analysis set, safety analysis set and pharmacokinetics analysis set, respectively. Statistical analysis methods will be detailed in the SAP.

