9.4.13. Electrocardiogram

Descriptive statistics for ECG parameters (eg, heart rate, PR interval, QRS interval, QT interval, and QTc interval [both Bazett's and Fridericia's corrections]) and changes from baseline at each protocol specified assessment time point will be presented. Select ECG parameters will be analyzed using a repeated measures analyses with dose and time points as factors and baseline ECG parameter as a covariate. Dose-response trend will be estimated.

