5. GENERAL CONSIDERATIONS FOR DATA ANALYSES AND HANDLING

5.1. General Summary Table and Individual Subject Data Listing Considerations

Descriptive statistics to be presented in a table include number of observations, mean, median, standard deviation, 1st and 3rd quartiles, minimum and maximum for continuous variables, and count of patients and the percentage for categorical variables. For variables that lognormal distribution assumptions may be appropriate geometric mean, and geometric coefficient of variation (CV%) will also be displayed. Geometric CV (%) will be derived as $100\% \times \sqrt{\exp(s^2) - 1}$, where s is the standard deviation of the natural logarithm (ln) transformed data.

For model-based analysis, least squares means (LSM), difference of least squares means between treatments, their standard errors and 95% confidence intervals (CI), and two-sided p-values for the statistical inferences will be presented.

Selected listings may be generated to include patient identifier (ID), demographics, randomized treatment group and other relevant items, and sorted by randomized treatment group, patient ID and date of assessment.

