8. SAFETY AND TOLERABILITY

Safety and tolerability analyses will be based on the Safety Analysis Set. Safety data will be analyzed descriptively and tabulated by treatment groups.

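### SAP 8.7 omits the repeated-measures ECG model of Protocol 9.4.13, and neither document prespecifies a baseline-adjusted arm difference in ECG intervals with a confidence interval

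*SAP*

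**What the plan says.** Protocol 9.4.13 asks for descriptive ECG statistics at each time point, with QTc under both the Bazett and Fridericia corrections. It then adds a model: "Select ECG parameters will be analyzed using a repeated measures analyses with dose and time points as factors and baseline ECG parameter as a covariate". The next sentence gives its target: "Dose-response trend will be estimated".

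SAP 8.7 plans interval summaries ("PR, RR, QRS, QT, and Fridericia corrected QT (QTcF) intervals and their change from baseline will be summarized by treatment group and scheduled assessment"), counts of patients in QTcF categories (the maximum-value categories by dosing group), and percentages with new morphology findings. The introduction to SAP Section 8 sets the general approach: "Safety data will be analyzed descriptively and tabulated by treatment groups". SAP 5.1 lists the contents of the descriptive tables for measured quantities: "Descriptive statistics to be presented in a table include number of observations, mean, median, standard deviation, 1st and 3rd quartiles, minimum and maximum for continuous". The list has no between-arm difference or confidence interval.

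On the relation between the documents, Protocol 9.4 says of the SAP that "it will include a more technical and detailed description of the statistical analyses described in this section".

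On how dose arises, Protocol 4.1 says: "Dose escalation at Weeks 2, 4, and 6 will occur only if a patient has a post-Valsalva LVOT-G" of at least 30 mmHg together with a biplane LVEF of at least 55%.

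**The concern.** There are two linked problems. First, the documents plan different ECG analyses, and the SAP, which is meant to elaborate the protocol's analyses, is silent about a model the protocol commits to. An analyst who follows the SAP leaves a protocol analysis undone. An analyst who follows the protocol runs something the SAP does not specify.

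Second, the protocol's model has dose as a factor and no term for randomized arm. Dose in this trial is a consequence of response. A patient reaches a higher dose because the gradient stayed high with LVEF preserved, so dose groups differ in ways that may also bear on ECG intervals. A difference between dose levels, or between one dose level and placebo, therefore does not carry the protection of randomization. The comparison that does is aficamten against placebo at each visit, and no baseline-adjusted estimate of it is planned for any ECG interval. ECGs in triplicate are collected at every visit, so the data for it will exist.

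**Working it through.** The plan states no figure on this point, so the check is mainly a comparison of texts.

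**1. Side by side**

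| Item | Protocol 9.4.13 | SAP 8.7 |
|---|---|---|
| Summaries of value and change | Yes | Yes, by arm and visit |
| Repeated-measures model | Yes, selected parameters | None |
| Model factors | Dose, time point, baseline | Not applicable |
| Dose-response trend | Yes | None |
| QT correction | Bazett and Fridericia | Fridericia only |
| Arm difference with CI | Not specified | Not specified |

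**2. Is the model elsewhere in the SAP?** The ECG models in SAP 7.9.1 are a Cox model for time to 1 mm ST depression and logistic models for the LVH strain pattern. The MMRM in that section serves continuous exploratory efficacy endpoints, and the list in SAP 2.2.3 contains no QT, PR or QRS interval. The sample code in SAP 11.5 has no ECG interval model. The SAP version history does not mention its omission.

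**3. Is the protocol text out of date?** No. SAP version 2 took effect on 9 October 2023. Protocol Amendment 04 is dated 8 December 2023 and still contains the model.

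**4. Could the protocol model yield the arm difference?** Protocol 9.4.1 says that model-based analyses report least-squares mean differences between treatments with 95% CIs, but the model in 9.4.13 has no treatment term. Coding placebo as dose zero does not solve this. Under Protocol 6.6.1, 6.6.2 and Table 4, a patient whose LVEF falls below 50% on 5 mg is switched to placebo. If dose is coded as the dose currently assigned, the zero-dose group would combine patients randomized to placebo with aficamten patients selected for low LVEF.

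**5. Precision of the missing contrast (illustration only).**
- Patients per arm: 135 (Protocol 9.2).
- With 10% missing, a rate the plan gives for the primary endpoint and which is borrowed here: 135 × 0.9 = 121.5.
- SD of QTcF change: not in the documents, assumed to be 10 to 25 ms.
- Half-width of the 95% CI at one visit: 1.96 × SD × √(2/n), where √(2/135) = 0.1217 and √(2/121.5) = 0.1283.

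| Assumed SD (ms) | 135 per arm (ms) | 121.5 per arm (ms) |
|---|---|---|
| 10 | 2.39 | 2.51 |
| 15 | 3.58 | 3.77 |
| 20 | 4.77 | 5.03 |
| 25 | 5.96 | 6.29 |

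The calculation is unadjusted. Adjustment for baseline should not widen the interval materially and may narrow it.

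**The case against.** The strongest reply is that safety analysis here is descriptive by design. No ECG interval is a listed safety endpoint, and laboratory data and vital signs get no arm-difference model either. SAP 8.7 already summarizes change by arm, and the safety set in SAP 5.5.3 is grouped by randomized arm apart from patients who received the other treatment throughout. A reader can compute an unadjusted difference and CI from n, mean and SD. This stands: what is missing is a prespecified, adjusted estimate, not the data or all sight of the randomized comparison. It does not remove the mismatch, because the protocol itself promised more than description.

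A second reply is that the protocol speaks only of selected parameters and does not say that QTcF is one of them. That also stands, so the omission cannot be described as a dropped QTcF model in particular.

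A third is that an arm-based model would say less than it seems to. The general visit order in Protocol 8.1 puts the ECG before dosing, so scheduled on-treatment ECGs give a difference at trough. A reader might infer that the triplicate ECGs would settle the drug's effect on QTcF throughout the dosing interval. The documents do not support that, and the result should be labelled accordingly.

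A reader might also infer that the dose-response trend would be seriously misleading and must be deleted. The documents give no dose distribution and no relation between gradient response and ECG change, so any distortion cannot be sized from them. Labelling the trend as non-randomized is enough.

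**Conclusion.** The point holds as a minor one. Protocol 9.4.13 and SAP 8.7 differ on the model, the trend and the QT correction, with no explanation, and the later document still contains the commitment. The protocol's dose factor follows post-randomization response, so its dose-level contrasts are not randomized comparisons. Neither document prespecifies a baseline-adjusted aficamten minus placebo difference with a CI for any ECG interval.

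These conclusions rest on the text alone. The precision figures, about 2.4 to 6.0 ms with 135 per arm and 2.5 to 6.3 ms with 10% missing, rest on an assumed SD and show only that the contrast could be estimated with useful precision.

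A reader might go further and conclude that the trial makes no randomized comparison of ECG intervals, or that its main conclusions are at risk. The by-arm summaries in SAP 8.7 contradict the first. The second fails because no primary or secondary efficacy test uses these data.

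**What to change.** In SAP 8.7, specify the following on the safety analysis set.

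- **Model:** change from baseline by repeated measures, using the MMRM code in SAP 11.5. Terms are randomized treatment, visit, treatment by visit, baseline, baseline by visit, beta-blocker use and exercise modality.
- **Parameters:** QTcF, QRS and heart rate. Add PR only for ECGs on which it is measurable, not those in atrial fibrillation. Protocol 4.1 allows persistent atrial fibrillation in up to about 15% of patients, so this rule is needed.
- **Output:** the aficamten minus placebo difference with 95% CI at each visit to Week 24, with a note that scheduled on-treatment ECGs are taken before dosing.
- **Relation to the protocol:** a sentence saying that this replaces the dose-factor model of 9.4.13. If a dose-response trend is kept, label it descriptive and non-randomized.
- **QT correction:** either add Bazett values to the SAP or state that Fridericia alone is used, and make the two documents agree.

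The cost is about one SAP paragraph using existing code. No new data are needed. SAP 5.4 already provides for a substantial change in analysis methods to be handled by a SAP revision or recorded in the study report. The protocol wording can be aligned if the protocol is amended again.

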9. PHARMACOKINETICS

Plasma concentrations of CK-3773274 and its measured metabolites and PK parameters $C_{\text{post dose}}$ and $C_{\text{pre-dose}}$ will be summarized using descriptive statistics including arithmetic mean, standard deviation, coefficient of variation, geometric mean, geometric coefficient of variation, median, and range. Geometric mean concentrations over time will be graphically displayed.

11. APPENDIX

11.1. Patient-reported Outcome Scoring Algorithm

11.1.1. KCCQ

There are 10 summary scores within the KCCQ, which are calculated as follows:

1. Physical Limitation

- Code responses to each of Questions 1a-f as follows:

Extremely limited = 1

Quite a bit limited = 2

Moderately limited = 3

Slightly limited = 4

Not at all limited = 5

Limited for other reasons or did not do = <missing value>

- If at least three of Questions 1a-f are not missing, then compute
Physical Limitation Score = $100 * [(\text{mean of Questions 1a-f actually answered}) - 1] / 4$
(see footnote at end of this appendix for explanation of meaning of “actually answered”)

2. Symptom Stability

- Code the response to Question 2 as follows:

Much worse = 1

Slightly worse = 2

Not changed = 3

Slightly better = 4

Much better = 5

I've had no symptoms over the last 2 weeks = 3

- If Question 2 is not missing, then compute
Symptom Stability Score = $100 * [(Question\ 2) - 1] / 4$

3. Symptom Frequency

- Code responses to Questions 3, 5, 7 and 9 as follows:

Question 3

Every morning = 1

3 or more times a week but not every day = 2

1-2 times a week = 3

Less than once a week = 4

Never over the past 2 weeks = 5

Questions 5 and 7

All of the time = 1

Several times a day = 2

At least once a day = 3

3 or more times a week but not every day = 4
1-2 times a week = 5
Less than once a week = 6
Never over the past 2 weeks = 7

Question 9

Every night = 1
3 or more times a week but not every day = 2
1-2 times a week = 3
Less than once a week = 4
Never over the past 2 weeks = 5

- If at least two of Questions 3, 5, 7 and 9 are not missing, then compute:

$$S3 = [(Question\ 3) - 1]/4$$

$$S5 = [(Question\ 5) - 1]/6$$

$$S7 = [(Question\ 7) - 1]/6$$

$$S9 = [(Question\ 9) - 1]/4$$

$$\text{Symptom Frequency Score} = 100 * (\text{mean of } S3, S5, S7 \text{ and } S9)$$

4. Symptom Burden

- Code responses to each of Questions 4, 6 and 8 as follows:

Extremely bothersome = 1

Quite a bit bothersome = 2

Moderately bothersome = 3

Slightly bothersome = 4

Not at all bothersome = 5

I've had no swelling/fatigue/shortness of breath = 5

- If at least one of Questions 4, 6 and 8 is not missing, then compute

$$\text{Symptom Burden Score} = 100 * [(\text{mean of Questions 4, 6 and 8 actually answered}) - 1]/4$$

5. Total Symptom Score

= mean of the following available summary scores:

Symptom Frequency Score

Symptom Burden Score

6. Self-efficacy

- Code responses to Questions 10 and 11 as follows:

Question 10

Not at all sure = 1

Not very sure = 2

Somewhat sure = 3

Mostly sure = 4

Completely sure = 5

Question 11

Do not understand at all = 1
Do not understand very well = 2
Somewhat understand = 3
Mostly understand = 4
Completely understand = 5

- If at least one of Questions 10 and 11 is not missing, then compute
Self-Efficacy Score = $100 * [(\text{mean of Questions 10 and 11 actually answered}) - 1] / 4$

7. Quality of Life

- Code responses to Questions 12, 13 and 14 as follows:

Question 12

It has extremely limited my enjoyment of life = 1
It has limited my enjoyment of life quite a bit = 2
It has moderately limited my enjoyment of life = 3
It has slightly limited my enjoyment of life = 4
It has not limited my enjoyment of life at all = 5

Question 13

Not at all satisfied = 1
Mostly dissatisfied = 2
Somewhat satisfied = 3
Mostly satisfied = 4
Completely satisfied = 5

Question 14

I felt that way all of the time = 1
I felt that way most of the time = 2
I occasionally felt that way = 3
I rarely felt that way = 4
I never felt that way = 5

- If at least one of Questions 12, 13 and 14 is not missing, then compute
Quality of Life Score = $100 * [(\text{mean of Questions 12, 13 and 14 actually answered}) - 1] / 4$

8. Social Limitation

- Code responses to each of Questions 15a-d as follows:

Severely limited = 1
Limited quite a bit = 2
Moderately limited = 3
Slightly limited = 4
Did not limit at all = 5
Does not apply or did not do for other reasons = <missing value>

- If at least two of Questions 15a-d are not missing, then compute

$$\text{Social Limitation Score} = 100 * [(\text{mean of Questions 15a-d actually answered}) - 1] / 4$$

9. Overall Summary Score

= mean of the following available summary scores:

Physical Limitation Score

Total Symptom Score

Quality of Life Score

Social Limitation Score

10. Clinical Summary Score

= mean of the following available summary scores:

Physical Limitation Score

Total Symptom Score

Note: references to “**means of questions actually answered**” imply the following.

- If there are n questions in a scale, and the subject must answer m to score the scale, but the subject answers only n-i, where $n-i \geq m$, calculate the **mean of those questions** as

$$(\text{sum of the responses to those } n-i \text{ questions}) / (n-i)$$

not

$$(\text{sum of the responses to those } n-i \text{ questions}) / n$$

11.1.2. SAQ-7

Three domain scores and one summary score are generated from the SAQ-7:

Physical Limitation Score (SAQ7-PL)

Angina Frequency Score (SAQ7-AF)

Quality of Life Score (SAQ7-QL)

Summary Score (SAQ7)

Scores are scaled 0-100, where 0 denotes the lowest reportable health status and 100 the highest.

Physical limitation Score

The physical Limitation score corresponds to Questions 1a, 1b and 1c. Responses are coded as follows:

Extremely limited	1
Quite a bit limited	2
Moderately limited	3
Slightly limited	4
Not at all limited	5
Limited for other reasons or did not do the activity	6

A response of 6 is treated as missing value for the purpose of scoring. If responses to two or more questions are missing, no score is computed. If the response to Question 1a or Question 1c is missing, it is assigned the responses from Question 1b. If the response to Question 1b is missing, it is assigned the average of responses to Questions 1a and 1c. The score is then calculated by taking the average of the three responses and rescaling to 0 – 100, as follows:

$$\text{SAQ7-PL} = 100 * [(\text{average of Questions 1a, 1b and 1c}) - 1] / 4$$

Angina Frequency Score

The Angina Frequency score corresponds to Questions 2 and 3. Responses are coded as follows:

4 or more times per day	1
1 – 3 times per day	2
3 or more times per week but not every day	3
1 -2 times per week	4
Less than once a week	5
None over the past 4 weeks	6

If responses to both questions are missing, no score is computed. Otherwise, the score is calculated by taking the average of non-missing responses and rescale to 0-100 as follows:

$$\text{SAQ7-AF} = 100 * [(\text{average of Questions 2 and 3}) - 1] / 5$$

Quality of Life Score

The quality of life score corresponds to Questions 4 and 5. Responses are coded as follows:

Question 4	
It has extremely limited my enjoyment of life	1
It has limited my enjoyment of life quite a bit	2
It has moderately limited my enjoyment of life	3
It has slightly limited my enjoyment of life	4
It has not limited my enjoyment of life at all	5
Question 5	
Not satisfied at all	1
Mostly dissatisfied	2
Somewhat satisfied	3
Mostly satisfied	4
Completely satisfied	5

If responses to both questions are missing, no score is computed. Otherwise, the score is calculated by taking the average of the non-missing response and rescaling to 0 -100, as follows:

$$\text{SAQ7-QL} = 100 * [(\text{average of Question 4 and 5}) - 1] / 4$$

Summary Score

The summary score represents an integration of the patients’ physical limitation, angina symptom and quality of life. If all three domain scores are missing, no summary score is computed. Otherwise, the score is calculated as the average of the non-missing domain scores:

$$\text{SAQ7} = \text{average of SAQ- PL, SAQ- AF, and SAQ – QL}$$

